### Warfarin Treated Group

If a patient experiences a major bleed warfarin should be temporarily stopped. The anticoagulant effect of VKAs can be reversed with vitamin K, prothrombin complex concentrates and/or fresh frozen plasma. Re-administration of warfarin after the bleeding has resolved and haemostasis has been achieved is at the discretion of the Investigator. Bridging therapy, e.g. UFH until the INR has returned back to the target range, is at the discretion of the Investigator (see Appendix [10.1](#)).

### 4.2.1.2 Minor Bleeds

If a patient experiences a minor bleed, trial medication may be continued, interrupted temporarily or permanently discontinued, at the discretion of the Investigator. It is not a requirement, however, that trial medication be stopped in these cases.

#### 4.2.1.3 Emergency and Elective Surgery

##### **Dabigatran Etexilate Treated Group**

###### Preoperative phase, Emergency Surgery:

In the case of emergency surgery, trial medication should be discontinued. If possible, surgery should be postponed until 12 hours, or longer in case of renal failure, after the last oral intake of trial medication.

In an emergency event, a measure of anticoagulation may become necessary to manage the situation. A physician may consider using the TT or diluted thrombin time (dTT) (where available), aPTT or ECT. For an adequate interpretation of the results the time of last intake of dabigatran etexilate needs to be known. For further details on results of coagulation times expected with dabigatran etexilate, see Section on elective surgery below.

If the condition is considered life threatening and surgery cannot be postponed, consider measures to reduce anticoagulation as described under major bleeds. See Section [4.2.1.1](#). In case of emergency surgery or urgent procedures when rapid reversal of the anticoagulation effect is required the specific reversal agent (idarucizumab) to dabigatran may be available in the context of a clinical trial, or from commercial supply depending on status of national authorization.

Reversing dabigatran therapy exposes patients to the thrombotic risk of their underlying disease. Dabigatran treatment can be re-initiated 24 hours after administration of idarucizumab, if the patient is clinically stable and adequate haemostasis has been achieved.

###### Preoperative phase, Elective Surgery:

Physicians may consider the following information regarding dabigatran etexilate when patients need to undergo surgery or elective procedures. Provided that the patient has normal renal function, the onset of effect of dabigatran etexilate is within 1 hour of dosing and dabigatran has peak concentrations 2-3 hours after an oral dose. Steady state is reached within 2-3 days. Plasma levels of dabigatran at steady state will vary across the population and are particularly affected by renal function. Patients with renal dysfunction may have elevated concentrations of dabigatran due to longer half-lives of active drug (see Table [4.2.1.3: 1](#)). Serum creatinine should normally be checked 1-2 weeks before surgery and the CrCl should be calculated using the Cockcroft-Gault formula (Section [5.3.3](#)). Patients with a CrCl <30mL/min during the course of this study should not be receiving trial medication (see Section [3.3.4.1](#)).

The following is a guide to the discontinuation of dabigatran etexilate (under special consideration of the half-life of dabigatran etexilate depending on renal function) before surgery taking renal function and additional risk factors into account. In patients with normal renal function, discontinuation of two doses of dabigatran etexilate will decrease plasma levels to approximately 25% of steady state trough levels and discontinuation of four doses will decrease dabigatran plasma levels to approximately 5-10% of steady-state trough levels.

Table 4.2.1.3: 1      Recommendations on cessation of trial medication in relation to the timing of major surgery

Renal function (CrCl, mL/min)	Estimated half- life if on dabigatran etexilate	Stop study dabigatran etexilate before surgery	
		High Risk of bleeding	Standard Risk
≥80	~ 13 hours	2 days before	24h prior (2 doses)
≥50 to <80	~ 15 (12-18) hours	2-3 days before	1-2 days before
≥30 to <50	~18 (18-24) hours	4 days before	At least 2 days (>48 hours)
<30	~ 27 (>24) hours	>5 days before	2-5 days

 CrCl can be estimated using serum creatinine by the Cockcroft-Gault formula (see Section 5.3.3). Patients who develop CrCl <30mL/min during the course of the trial should have trial medication stopped (see Section 3.3.4.1).

 In addition to renal function, high risk determinants of bleeding risk include type of surgery, advancing age, comorbidities (e.g. major cardiac, respiratory or liver disease) and concomitant use of antiplatelet therapy. The type of surgery associated with a high risk of bleeding includes but is not limited to cardiac surgery, neurosurgery, abdominal surgery or those involving a major organ. Other procedures such as spinal anaesthesia may also require complete haemostatic function.

The clinician should consider delaying surgery in patients at high risk of bleeding, including those in whom severe renal dysfunction may occur in the course of the trial (<30mL/min CrCl), an elevated TT or dTT (dTT only in countries where this assay is approved). If the TT/dTT test is not available, an aPTT, though less precise than the TT, can be used.

A TT/dTT should be performed 6-12 hours before elective surgery and a normal result as defined by the local lab should be obtained before a patient undergoes surgery. A persistently prolonged thrombin time (TT or dTT) in the absence of heparin, fibrin/fibrinogen degradation products (e.g. with disseminated coagulation activation, sepsis, severe inflammation and other conditions) or high concentrations of serum proteins (e.g. myeloma) suggests persistently elevated levels of dabigatran in the blood.

In patients receiving chronic therapy with dabigatran etexilate 150 mg b.i.d., the median peak aPTT is approximately 63 sec . Assuming the baseline range of normal is between 22 to 40 sec (aPTT assay as used in RE-LY) this peak aPTT prolongation corresponds to approximately 1.5 times the upper limit of normal . Twelve hours after the last dose, the median aPTT is approx. 1.3 times upper limit of normal (median trough aPTT prolongation for patients receiving 150 mg b.i.d. in RE-LY: 51.9 sec), with less than 10% of patients exceeding 2 times upper limit of normal (90th percentile trough aPTT prolongation for patients receiving 150 mg b.i.d. in RE-LY: 76.4 sec)

ECT shows a linear correlation with the plasma concentrations of direct thrombin inhibitors, including dabigatran. Median ECT ratios over baseline (median baseline: 30.3 sec) of approx. 2.1 at trough (median trough ECT prolongation for patients receiving 150 mg b.i.d. in RE-LY: 62.9 sec) and 3.0 at peak (median peak ECT prolongation for patients receiving 150 mg b.i.d. in RE-LY: 92.9 sec) have been observed after intake of dabigatran etexilate 150 mg b.i.d . Twelve hours after the last dose, less than 10% exceed a ratio of 3.5 from baseline (90th percentile of trough ECT for patients receiving 150 mg b.i.d. as observed

in RE-LY: 103 s) Coagulation times should always be interpreted in relation to the timing of last drug intake of trial medication (peak versus trough dabigatran levels). The current version of the IB should be referenced for further information about dabigatran etexilate.

**Post-procedural Period:**

With the exception of cardiac surgery, dabigatran etexilate will be initiated as soon as the patient is haemodynamically stable and haemostasis is achieved. If oral medication is not feasible, bridging therapy with i.v. or s.c. UFH or s.c. LMWH should be considered at the discretion of the Investigator (see Appendix [10.1](#)).

Note: In patients where renal function is impaired or procedures undertaken which may temporarily compromise renal function, a serum creatinine should be performed and CrCl calculated based on the Cockcroft-Gault formula. See Section [3.3.4.1](#) for how to handle patients receiving dabigatran etexilate and for whom CrCl drops to <30 mL/min during the course of the study.

**Warfarin Treated Group**

**Preoperative Phase**

Bridging therapy with a parenteral anticoagulant should be considered depending on the length of trial medication interruption. Bridging therapy is at the discretion of the Investigator and can be performed according to local practice (see Appendix 10.1 for guidance).

**Post-procedural Period**

Anticoagulation can be started as soon as clinically feasible with i.v. (unfractionated) heparin or s.c. LMWH and simultaneously with study warfarin until the INR is  $\geq 2.0$ . Parenteral bridging therapy should be stopped when target INR is achieved (see Appendix 10.1 for guidance).

**4.2.1.4 Spinal Anaesthesia/Epidural Anaesthesia/Lumbar Puncture**

**Dabigatran etexilate and Warfarin Treated Group**

Procedures such as spinal anaesthesia may require complete haemostatic function. See Table [4.2.1.3: 1](#) for recommendations on when to stop dabigatran before spinal/epidural anaesthesia. For patients randomised to Warfarin, INR measurements should be performed to ensure that coagulation is under control.

The risk of spinal or epidural haematoma may be increased in cases of traumatic or repeated puncture and by the prolonged use of epidural catheters. After removal of a catheter, resume treatment with trial medication after complete haemostasis is achieved, but at minimum an interval of one hour should elapse for all patients. These patients require frequent observation for neurological signs and symptoms of spinal or epidural haematoma.

**4.2.1.5 Stroke of non-CVT origin**

Patients with documented or suspected stroke of non-CVT origin should be managed according to usual clinical practice. It is anticipated that in most cases trial medication will be

withheld until a CT or MRI scan has been obtained and diagnosis has been made. For recommendations regarding a new CVT or worsening of symptoms of the index CVT, refer to Section [4.2.1.6](#).

### **Ischaemic stroke**

For ischaemic stroke usual clinical practice may be followed, which may include administration of ASA and/or clopidogrel, or ASA/dipyridamole (the latter in lieu of clopidogrel). The decision whether or not to continue administration of the trial medication is at the discretion of the local Investigator, also taking into account the possible presence of bleeding [[P13-06400](#)].

Fibrinolitics may be considered for ischaemic stroke, if the patient presents with a TT, dTT, ECT, or (if TT, dTT or ECT are not available) an aPTT lab result not exceeding the upper limit of normal (ULN) according to the local reference range for patients receiving dabigatran etexilate, or if the INR is  $\leq 1.7$  in patients receiving warfarin.

### **Haemorrhagic stroke**

For haemorrhagic stroke (not directly related to CVT) or other intracranial bleeding, consultation with a coagulation expert and a neurosurgeon is recommended. See Section [4.2.1.1](#) and Figure [4.2.1.1: 1](#) for details relating to how to manage bleeding on dabigatran etexilate or warfarin.

### **Reintroduction of trial treatment following a stroke**

#### **Dabigatran Etexilate Treated Group**

The decision for restarting dabigatran etexilate following a stroke is at the discretion of the Investigator. For the timing of restarting anticoagulation after stroke event clinical recommendations should be consulted [[P12-02400](#)]. The following recommendations on when to restart dabigatran etexilate are provided for guidance only: In general, dabigatran etexilate can be restarted after a TIA as soon as imaging has excluded a cerebral haemorrhage. For mild, moderate and severe stroke, expert recommendations [[P12-02400](#)] suggest restarting dabigatran etexilate 3-5 days, 5-7 days, and 2 weeks after stroke onset, respectively.

#### **Warfarin Treated Group**

The decision for restarting study warfarin following a stroke and its exact timing is at the discretion of the Investigator.

#### **4.2.1.6 Venous thrombotic event (VTE)**

#### **CVT**

A new event of CVT occurring during the trial treatment period, as well as worsening symptoms such as an ischaemic stroke as a result of the index CVT, should be treated according to current AHA/ASA and EFNS guidelines [[R15-5005](#); [P10-11802](#)]. Trial treatment should be interrupted while the patient is being treated with other antithrombotic therapy or with other medication that is restricted per Section [4.2.2.1](#). The decision for restarting trial treatment is at the discretion of the Investigator.

### **DVT, PE or splanchnic vein thrombosis**

An event of DVT, PE or splanchnic vein thrombosis occurring during the trial treatment period should be treated according to local clinical practice. Trial treatment should be interrupted if the patient is being treated with other anticoagulation therapy or with other medication that is restricted per Section [4.2.2.1](#). The decision for restarting trial treatment is at the discretion of the Investigator.

#### 4.2.1.7      Renal failure

See Section [3.3.4.1](#) for instructions in case CrCl drops to below 30mL/min in a patient randomised to receive dabigatran etexilate.

#### 4.2.1.8      Other Medical Intervention

### **Other Minor Procedures:**

#### **Dabigatran Etexilate Treated Group**

In the case of other elective procedures or minor surgery, dabigatran etexilate can be continued until 24 hours before the procedure. For the timing of treatment interruption before the procedure see also Table [4.2.1.3: 1](#).

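### For dabigatran patients with CrCl 30 to <50 mL/min, the 24-hour stop in protocol Section 4.2.1.8 and the table that section cites cannot both be followed

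*Protocol*

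**What the plan says.** Section 4.2.1.8 of the protocol (Other Minor Procedures, dabigatran group) has two sentences. The first says that, for minor surgery and other elective procedures, "dabigatran etexilate can be continued until 24 hours before the procedure". It has no condition on renal function or bleeding risk. The second begins "For the timing of treatment interruption before the procedure see also Table" and points to Table 4.2.1.3: 1.

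That table stands in Section 4.2.1.3 under elective surgery and is titled "Recommendations on cessation of trial medication in relation to the timing of major surgery". The text above it presents the information as something physicians may consider "when patients need to undergo surgery or elective procedures" and calls it a guide that takes renal function into account. In its standard-risk column the table gives:

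- CrCl ≥80: "24h prior (2 doses")
- CrCl 50 to <80: "1-2 days before"
- CrCl 30 to <50: "At least 2 days (>48 hours")

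Section 4.2.1.4 also sends the reader to this table, for stopping dabigatran before spinal or epidural anaesthesia. Exclusion criterion 8 in Section 3.3.3 removes patients with CrCl below 30 mL/min at screening and those expected to fall below 30 during the study. Patients with CrCl 30 to <50 may therefore be randomised.

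**The concern.** A site preparing a dabigatran patient with, say, CrCl 40 mL/min for a minor elective procedure reads one paragraph and gets two answers: 24 hours from the sentence itself, and more than 48 hours from the table it cites. Nothing in the paragraph ranks the two.

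This is first a matter of participant safety. Interruption before a procedure balances bleeding against thrombosis, and the protocol should not leave two sites free to treat the same patient differently while both follow the text. It is also a matter of conduct, since a monitor could not say which of the two sites had departed from the protocol.

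**Working it through.** No power, sample-size or alpha figure is involved. The check compares the two texts row by row and then uses the table's own half-lives to see whether renal function makes a material difference.

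**Row-by-row comparison, standard bleeding risk**

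| CrCl (mL/min) | Section 4.2.1.8 | Table 4.2.1.3: 1 | Result |
|---|---|---|---|
| ≥80 | 24 h | 24 h | agree |
| 50 to <80 | 24 h | 1–2 days (24–48 h) | overlap at the lower end |
| 30 to <50 | 24 h | more than 48 h | cannot both be followed |

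The table's row for CrCl below 30 is left out, because Section 3.3.4.1 has dabigatran withheld or stopped in those patients. In the high-risk column (2 days, 2–3 days and 4 days for the three rows above), 24 h is shorter throughout. That column is driven partly by the type of surgery, so the standard-risk column is the fairer comparison for minor procedures.

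**Does the protocol's own pharmacology distinguish these rows?**

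Inputs, all from Section 4.2.1.3:
- half-life about 13 h for CrCl ≥80
- half-life about 15 h (12–18) for CrCl 50 to <80
- half-life about 18 h (18–24) for CrCl 30 to <50
- with normal renal function, about 25% of the steady-state trough level remains after two omitted doses, and about 5–10% after four

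Assumption: first-order decay, so the fraction remaining = 0.5^(t / half-life).

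Reproducing the protocol's figures first (two doses = 24 h, four doses = 48 h, half-life 13 h):
- 0.5^(24/13) = 27.8%, against about 25% stated
- 0.5^(48/13) = 7.7%, against 5–10% stated

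The simple model therefore matches the protocol closely enough to use.

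Applying it to the other rows:
- CrCl 50 to <80 at 24 h: 25.0% (12 h half-life), 33.0% (15 h), 39.7% (18 h)
- CrCl 30 to <50 at 24 h: 39.7% (18 h), 50.0% (24 h)
- CrCl 30 to <50 at 48 h: 15.7% (18 h), 25.0% (24 h)

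At CrCl 30 to <50, the ratio of the 24 h residual to the 48 h residual is 39.7/15.7 = 2.5 with an 18 h half-life and 50.0/25.0 = 2.0 with a 24 h half-life. On the protocol's own figures, then, the two instructions lead to clearly different drug levels in this group, and the 25% figure quoted for normal renal function does not carry over to it. This shows that the discrepancy is more than a rounding of days. It does not show which timing is appropriate.

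**The case against.** The best defence is that the two texts have different scopes. The table is titled for major surgery, so a shorter general figure for minor procedures may be deliberate. Both texts are also soft: the table is a guide made up of recommendations, and the 24-hour sentence is permissive. On a charitable reading, 24 hours is a general figure that the table then refines.

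Part of this stands. The table recommends rather than requires, and Section 4.2.1.8 covers other elective procedures and minor surgery, not every procedure. At CrCl 50 to <80 there is no strict conflict.

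The scope defence does not remove the problem. The lead-in to the table covers elective procedures as well as surgery, Section 4.2.1.4 uses the table for spinal and epidural anaesthesia, and Section 4.2.1.8 cites it for the very procedures to which it would supposedly not apply. If the table refines the 24-hour figure, the text should say so; if it does not apply, the cross-reference misleads.

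A reader might also infer bias in the primary endpoint: a procedural bleed with a haemoglobin fall of at least 2 g/dL counts as a major bleed, and one event among 60 patients is 1/60 = 1.7 percentage points against an assumed 2–3% event rate. The documents do not support that inference. The 1.7 points hold for any single event in an arm of 60, and nothing in the documents gives a probability that this instruction would cause one. Procedural bleeds can also occur on warfarin, and a bleed on dabigatran around a procedure may be a genuine outcome of treatment. Only the conflicting instruction is specific to the dabigatran arm.

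**Conclusion.** The inconsistency is real and narrow. For eligible dabigatran patients with CrCl 30 to <50 mL/min at standard bleeding risk, Section 4.2.1.8 allows dosing until 24 hours before a minor procedure, while the table it cites gives more than 48 hours, and the protocol does not say which prevails.

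The number affected is probably small. Section 1.1 reports a mean age of 39 years in the international CVT cohort and fewer than 10% of patients over 65. The conflict needs a patient in this CrCl band, in a dabigatran arm of 60, who has a minor elective procedure within 24 weeks. The documents give no count of such patients, and none is assumed here. Sample size, estimand and analysis are unaffected. The point merits correction because it concerns a safety instruction and is cheap to put right.

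A reader might go on to conclude that the table is right and the 24-hour sentence unsafe. The documents do not establish that; they show only that the two disagree.

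**What to change.** Reconcile Section 4.2.1.8 with Table 4.2.1.3: 1 so that sites have a single instruction for minor procedures in patients with reduced CrCl. State explicitly whether the table governs minor procedures, and bring its title into line with the uses that Sections 4.2.1.3, 4.2.1.4 and 4.2.1.8 make of it. The interruption time itself is a clinical decision for the sponsor, and no timing is proposed here.

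The cost is a change to one sentence and one table title, made through the usual amendment route and notified to sites. The SAP needs no change.

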#### **Warfarin Treated Group**

For patients randomised to Warfarin, refer to Section [4.2.1.3](#).

### **Reintroduction following medical intervention**

#### **Dabigatran Etexilate Treated Group**

Dabigatran etexilate can be re-commenced at the cessation of parenteral anticoagulant treatment according to the same regimen as at randomisation, provided clinically indicated and in accordance with the recommendations in Appendix [10.1](#).

#### **Warfarin Treated Group**

For patients randomised to Warfarin, refer to Section 4.2.1.3.

#### 4.2.1.9      Overdose

Overdose following administration of dabigatran etexilate may lead to haemorrhagic complications due to its pharmacodynamic properties. In cases of suspected overdose it may be advisable to assess the anticoagulation status of a patient. A TT measure with the calibrated Hemoclot® thrombin inhibitor assay indicating a dabigatran plasma concentration of >200ng/mL (approximately >65 seconds) prior to the next drug intake after 150 mg twice-daily dosing (trough measure, i.e. 10-16 hours after the last drug intake) may be associated with an increased risk of bleeding. An aPTT test may be useful to assist in determining an excess of anticoagulant activity, despite its limited sensitivity. An aPTT > 2-fold ULN at trough, i.e. when the next dose is due, may be associated with a higher risk of bleeding. For a summary how to manage bleeding events on dabigatran etexilate see also Section [4.2.1.1](#) and corresponding Figure [4.2.1.1: 1](#).

If an overdose is associated with bleeding, see the advice given in Section [4.2.1.1](#), and [4.2.1.2](#).

## **4.2.2      Restrictions**

### **4.2.2.1      Restrictions regarding concomitant treatment**

The following treatments should not be taken during the active treatment phase of the trial:

- Fibrinolytic agents (see Section [4.2.1.5](#) for exceptions)
- GPIIb/IIIa antagonists (e.g. abciximab, tirofiban)
- Rivaroxaban, apixaban and edoxaban, or other oral anticoagulants (e.g. VKAs)
- Treatment with systemic ketoconazole, itraconazole, posaconazole, cyclosporine, tacrolimus and dronedarone, and rifampicin, carbamazepine, phenytoin and St. John's Wort
- Any type of dual antiplatelet therapy

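### After a non-CVT ischaemic stroke, Protocol 4.2.1.5 allows two antiplatelet agents and leaves trial drug to the investigator, without tying this to the dual-antiplatelet ban in 4.2.2.1

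*Protocol*

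**What the plan says.** Protocol Section 4.2.2.1 lists treatments that patients should not take in the active treatment phase. The last item is "Any type of dual antiplatelet therapy". No exception is attached to it. The fibrinolytic item in the same list does carry one, and it points to Section 4.2.1.5.

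Section 4.2.1.5 covers stroke of non-CVT origin. It expects trial drug to be held back in most cases until a scan and a diagnosis are available. For ischaemic stroke it then allows usual practice, "which may include administration of ASA and/or clopidogrel, or ASA/dipyridamole". On trial drug it says: "The decision whether or not to continue administration of the trial medication is at the discretion of the local Investigator". The only factor it goes on to name is bleeding: "also taking into account the possible presence of bleeding". Restart is also left open in each arm: "The decision for restarting dabigatran etexilate following a stroke is at the discretion of the Investigator" and "The decision for restarting study warfarin following a stroke and its exact timing is at the discretion of the Investigator". For dabigatran it adds suggested restart times of 3-5 days, 5-7 days and 2 weeks by stroke severity, as guidance only.

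Section 4.2.1.6 covers venous thrombotic events and does link trial drug to the restricted list; both sentences below end by citing 4.2.2.1. For a new CVT, or worsening from the index CVT: "Trial treatment should be interrupted while the patient is being treated with other antithrombotic therapy or with other medication that is restricted per Section". For DVT, PE or splanchnic vein thrombosis: "Trial treatment should be interrupted if the patient is being treated with other anticoagulation therapy or with other medication that is restricted per Section".

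**The concern.** A site managing a non-CVT ischaemic stroke will turn to Section 4.2.1.5. There it finds permission to use two antiplatelet agents, followed by discretion over trial drug. It finds nothing to say that the two permissions may not be used together. The combination of an anticoagulant with two antiplatelet agents is what 4.2.2.1 rules out.

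What is at stake is bleeding safety. Section 1.2 reports that, in the atrial fibrillation trial of dabigatran against warfarin, bleeding risk was about twice as high when ASA or clopidogrel was added, in both dabigatran-treated and warfarin-treated patients. The documents give no figure for two agents on top of an anticoagulant, so only the direction of the hazard can be taken from them.

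**Working it through.** No sample size, power or event figure is involved, so the check is a comparison of texts.

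1. **Does the ban cover the regimens named in 4.2.1.5?** The phrase ASA and/or clopidogrel includes single-agent use, which Section 4.2.2.2 allows with caution when clinically indicated. That branch raises no conflict. ASA with clopidogrel is a two-agent regimen. So is ASA/dipyridamole, which the text offers in place of clopidogrel. Because 4.2.2.1 speaks of any type, I read it as covering both.

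2. **Is there an exception?** Not for this item. Only fibrinolytics are referred to 4.2.1.5.

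3. **Does 4.2.1.5 itself keep the two apart?** It expects trial drug to be withheld initially, but as an expectation for most cases, and only up to imaging and diagnosis. After that, continuation and restart are discretionary. The one consideration named for continuation is possible bleeding. No sentence makes either decision depend on whether dual therapy is under way or has ended.

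4. **How does the neighbouring section handle it?** Counting the event paragraphs that tie interruption of trial drug to medication restricted per 4.2.2.1:

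| Section | Events covered | Statements of the rule |
|---|---|---|
| 4.2.1.6 | CVT; DVT, PE or splanchnic vein thrombosis | 2 of 2 event paragraphs |
| 4.2.1.5 | Stroke of non-CVT origin | 0 |

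Section 4.2.1.6 also leaves restart to the investigator, but only after saying that treatment should be interrupted.

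5. **Does other text close the gap?**
- Section 2.3 lists as a safeguard that drugs interacting with either trial medication are forbidden. This is a broad statement and does not mention antiplatelets or stroke.
- Section 3.3.4.1 requires withdrawal from trial treatment when a patient needs drugs that interfere with it, and cites Section 4.2.2. The term is not defined, and 4.2.2 also contains single antiplatelets that are allowed with caution.
- Section 4.2 says certain therapies may call for a temporary stop. Its drug examples are fibrinolytics and other anticoagulants.
- Exclusion criterion 9 and the Visit 2 instruction in Section 6.2.2 apply at entry, not to a stroke during the trial.

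6. **How wide is the gap?** Ischaemic stroke resulting from the index CVT already falls under 4.2.1.6. Only non-CVT ischaemic stroke treated with two antiplatelet agents is left.

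**The case against.** The strongest reply is that this is a missing cross-reference and not a contradiction. The ban in 4.2.2.1 is itself an in-trial rule, and a patient kept on trial drug after a stroke is still in the active treatment phase. Section 4.2.1.5 allows antiplatelets as stroke care and, separately, gives discretion over trial drug. If the investigator stops trial drug while two agents are given, both sections are respected. The withdrawal rule in 3.3.4.1 is mandatory and points the same way. Section 4.2.1.5 also cites practical guidance on anticoagulant use, and recommendations on restart timing; what those sources say about dual therapy cannot be seen here.

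Much of this stands. A reader might infer that the protocol authorises trial drug together with dual antiplatelet therapy. The documents do not support that, because nothing in 4.2.1.5 lifts the ban and the sections can be reconciled. A reader might also infer that trial drug is expected to run on unbroken through the stroke. That is not supported either, given the expected hold until diagnosis.

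What remains is that the reconciling step is not written where the site will look. The specific discretion in the stroke section would naturally be read as overriding general text elsewhere.

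A second objection concerns the remedy. In 4.2.1.6, interruption goes with other antithrombotic or anticoagulant treatment. After a non-CVT stroke, interrupting trial drug for dual antiplatelet therapy could leave a CVT patient without an anticoagulant. If the gap is bridged parenterally, as Sections 4.2 and 10.1.3 allow, the patient again receives an anticoagulant with two antiplatelet agents. This is fair, and the fix has to address it. An exception in 4.2.2.1 for dual therapy after stroke would also remove the mismatch, but by loosening the ban.

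**Conclusion.** The point holds as a minor inconsistency in a safety instruction. Section 4.2.2.1 bans dual antiplatelet therapy during active treatment without exception. Section 4.2.1.5 permits two-agent regimens and, beyond the initial hold, leaves trial drug to the investigator without reference to that ban. Sections 2.3 and 3.3.4.1 lean towards separation but do not settle it.

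Its size cannot be expressed as a risk. The documents give no rate of non-CVT ischaemic stroke, no rate of dual antiplatelet use, and no bleeding risk for the combination. It should be rare: 120 patients followed over 24 weeks, in a disease where Section 1.1 gives a mean age of 39 years in the international cohort and fewer than 10% of patients above 65. The count of 2 against 0 shows where the rule is stated; it does not measure harm.

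A reader might go on to infer bias between arms or damage to the primary result. Nothing supports this. Continuation and restart are discretionary in both arms, and the primary analysis keeps all randomised patients in their assigned group whatever medication they took.

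The conclusion assumes that ASA/dipyridamole counts as dual antiplatelet therapy and that the ban in 4.2.2.1 reflects the sponsor's intention.

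**What to change.** Add to Section 4.2.1.5, for both arms, wording along these lines: *While trial medication is continued or restarted, no more than one antiplatelet agent may be given (see Sections 4.2.2.1 and 4.2.2.2). If two agents are judged necessary, trial medication is interrupted and not restarted until dual therapy has ended. Any parenteral bridging in that period should be weighed against the bleeding risk.*

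This enforces the existing ban and follows the pattern of 4.2.1.6. It needs a short protocol amendment and no new data, visits or analyses. The clinical cost is that a patient who needs dual therapy may have a gap in CVT anticoagulation. The present ban already implies that gap; the added text makes it explicit, so that the investigator can plan for it.
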